14.4 Reporting Procedures

Serious AEs and Unexpected AEs are to be reported to the CHR within 10 working days after first becoming aware of the event.

Adverse events that are *unanticipated* (see definition above) will be reported in writing to the CHR and FDA as soon as possible but no later than 10 working days after first becoming aware of the event [21 CFR 812.150(a) (1) and 21 CFR 812.50(b) (1)]. A copy of the CHR report should be forwarded to the manufacturer of the device at the address below:

Biocompatibles UK Limited
[name]
[name]
[name]
[name]
[contact]
[contact]

A copy of the CHR forms must be sent to the CCC DSMC at [name]. If the AE is a death attributed as at least possibly-related to study drug or treatment during the treatment phase of the study or within 30 days after the last DEB-TACE procedure, it must be reported to the CCC DSMC Chair (or qualified alternate) within 1 business day of knowledge of the event (*see section 13.4*). The contact may be by phone or e-mail. The date the safety report was sent to all required reporting agencies will be documented on the OnCore® database, and hard copies of the report will be maintained in the regulatory files.

15.0 Protection of Human Subjects

15.1 Protection from Unnecessary Harm

Each clinical site is responsible for protecting all subjects involved in human experimentation. This is accomplished through the CHR mechanism and the process of informed consent. The CHR reviews all proposed studies involving human experimentation and ensures that the subject's rights and welfare are protected and that the potential benefits and/or the importance of the knowledge to be gained outweigh the risks to the individual. The CHR also reviews the informed consent document associated with each study in order to ensure that the consent document accurately and clearly communicates the nature of the research to be done and its associated risks and benefits.

15.2 Protection of Privacy

Patients will be informed of the extent to which their confidential health information generated from this study may be used for research purposes. Following this discussion, they will be asked to sign the HIPAA form and informed consent documents. The original signed document will become part of the patient's medical records, and each patient will receive a copy of the signed document. The use and disclosure of protected health information will be limited to the individuals described in the informed consent document.

16.0 FINANCIAL CONSIDERATIONS

The costs of treatment will be charged to the subject and/or their insurance company.

Appendix 1 ECOG Performance Status Criteria

ECOG Performance Status Scale	
Grade	Descriptions
0	Normal activity Fully active, able to carry on all pre-disease performance without restriction
1	Symptoms, but ambulatory Restricted in physically strenuous activity, but ambulatory and able to carry out work of a light or sedentary nature (e.g., light housework, office work)
2	In bed < 50% of the time Ambulatory and capable of all self-care, but unable to carry out any work activities Up and about more than 50% of waking hours
3	In bed > 50% of the time Capable of only limited self-care, confined to bed or chair more than 50% of waking hours
4	100% bedridden Completely disabled Cannot carry on any self-care Totally confined to bed or chair
5	Dead

Appendix 2 Child-Pugh Score

<http://homepage.mac.com/sholland/contrivances/childpugh.html>

Below is an example of a calculated score:

Naperville Gastroenterology

[name], FACP
[name]
[name]

Child-Pugh Score Calculator

Bilirubin: <2 mg/dl (34 umol/l) 2-3 mg/dl (34-50 umol/l) >3 mg/dl (50 umol/l)

Albumin: >3.5 g/dl 3.5-2.8 <2.8

PT prolongation (INR): <4 seconds (<1.7)

4-6 seconds (1.7-2.3)

>6 seconds (>2.3)

Ascites: Absent Mild-Moderate Severe/Refractory

Encephalopathy: Absent Mild (I-II) Severe (III-IV)

Child-Pugh Score:

Interpretation:

Class A: 5-6

Class B: 7-9

Class C: 10-15

This calculator is Copyright 2003, [[name].](#)

Naperville Gastroenterology, [name]

Permission is granted to use this calculator. Please eMail me to request permission for other use.

This calculator is kept at <http://napervillegi.com/contrivances/childpugh.html>

Appendix 3 MELD Score

<http://www.mayoclinic.org/meld/mayomodel6.html>

The MELD Model, UNOS Modification

In the following model, survival probability of a patient with end-stage liver disease is estimated based on the following variables. Please enter data in the corresponding boxes.

What is the INR?

What is the bilirubin? (mg/dl)

What is the creatinine? (mg/dl)

Has the patient had dialysis at least twice in the past week? No
Yes

MELD score:

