4. Hepatic progression-free survival (HPFS). Hepatic progression-free survival rate will be defined as the number of patients who neither progressed in the treated regions of the liver (using RECIST 1.1 and mRECIST) nor died before 1, 3, 6, 9, and 12 months after date of last DEB-TACE over the number of patients who entered the trial at these same timepoints. Estimates of the HPFS curves from the Kaplan-Meier method will be presented. Median progression event time and a 2-sided 95% confidence interval for the median will be provided using a normal approximation. For each stratum, the median, 25th and 75th percentile for HPFS will be provided.
5. Progression-free survival (PFS). Progression-free survival rate will be defined as the number of patients who neither progressed (using RECIST 1.1 and mRECIST) nor died before 1, 3, 6, 9, and 12 months after date of last DEB-TACE over the number of patients who entered the trial at these same timepoints. Estimates of the PFS curves from the Kaplan-Meier method will be presented. Median progression event time and a 2-sided 95% confidence interval for the median will be provided using a normal approximation. For each stratum, the median, 25th and 75th percentile for PFS will be provided.
6. Overall Survival (OS) is a secondary efficacy endpoint and will be analyzed 12 months after the last patient is enrolled. OS will be calculated from date of first DEB-TACE until date of death, using chart review and/or follow up phone calls to determine date of death in patients after removal from study. The survival of patients who are permanently lost to follow-up or still alive after 360 days of follow up post study discontinuation will be censored on the date the patient is last-contacted or last known to be alive. Estimates of the OS curves from the Kaplan-Meier method will be presented.
7. Proportion of patients who remain active on the waitlist and are eventually transplanted is a secondary clinical endpoint. This data will be presented using Kaplan-Meier method
8. Proportion of patients who are inactivated or drop out from the wait list for any reason but transplantation will be determined. Reasons for inactivation and/or removal from waitlist will be tabulated.
9. Proportions of patients who are successfully down-staged and achieve active waitlist status and eventually are transplanted will be determined.

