10. Biochemical response defined as $\geq 50\%$ decrease in alpha-fetoprotein level measured 1 month and 4 months after DEB-TACE.
11. Histopathologic response defined as percentage of tumor necrosis at liver explant histopathology. This will only be explored in the subgroup of patients who undergo a liver transplant. Per UCSF clinical standard, tumor necrosis for HCC lesions is reported as 100%, >90%, 60-90%, 30-59%, and < 30%.

Intention To Treat Exceptions (Patient replacement)

1. Patients who proceed to liver transplant or develop hepatic decompensation between the time of enrollment and the first DEB-TACE treatment will be replaced.
2. Patients who proceed to liver transplant prior to completion of the 1 month safety window after first DEB-TACE will be replaced unless the transplant occurred due to hepatic decompensation or other toxicity attributed as at least possibly-related to protocol therapy, in which case the hepatic decompensation or other toxicity will be deemed a serious adverse event and the patient will be included in safety analysis (see Section 14.1.3).

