14.1.3 Serious Adverse Events

A serious adverse event (SAE) is one that results in any of the following outcomes regardless of dose:

- Death
- Life-threatening (places the subject, in the view of the investigator, at immediate risk of death from the reaction as it occurred), including hepatic decompensation requiring hospitalization or expedited liver transplantation
- Inpatient hospitalization or prolongs existing hospitalization,
- Persistent or significant disability/incapacity (a substantial disruption of a person’s ability to conduct normal life functions),
- Birth defect/congenital anomaly,
- Any important medical event that may not result in prior listed outcomes but, based upon appropriate medical judgment, may jeopardize the subject, and may require medical or surgical intervention to prevent one of the prior listed outcomes.

An adverse event is not considered serious if it does not satisfy at least one of these criteria.

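### Section 12.3 items 7 and 8 do not separate transplants caused by treatment-related decompensation from planned bridge transplants

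*Combined protocol and SAP*

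**What the plan says.** **Endpoints.** Section 12.3 lists three waitlist outcomes among its secondary efficacy analyses.

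- Item 7: "Proportion of patients who remain active on the waitlist and are eventually transplanted is a secondary clinical endpoint". The method is one sentence: "This data will be presented using Kaplan-Meier method".
- Item 8: "Proportion of patients who are inactivated or drop out from the wait list for any reason but transplantation will be determined". Reasons for inactivation or removal are to be tabulated; reasons for transplant are not.
- Item 9: "Proportions of patients who are successfully down-staged and achieve active waitlist status and eventually are transplanted will be determined".

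**Replacement.** Under the intention-to-treat exceptions in the same section, exception 2 says that patients transplanted before the one-month safety window after the first DEB-TACE has closed "will be replaced unless the transplant occurred due to hepatic decompensation or other toxicity attributed as at least possibly-related to protocol therapy". For those who are not replaced, "the hepatic decompensation or other toxicity will be deemed a serious adverse event and the patient will be included in safety analysis".

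**The same event elsewhere.** Section 14.1.3 puts it in the life-threatening class of serious adverse events, "including hepatic decompensation requiring hospitalization or expedited liver transplantation". Section 10.1.1 combines death and urgent transplant into one adverse outcome when it justifies the safety rules. Section 1.2 names urgent transplant beside death as a consequence of irreversible decompensation.

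**Appendix 3.** The MELD appendix opens with "In the following model, survival probability of a patient with end-stage liver disease is estimated based on the following variables" and then lists the calculator's inputs. It gives no rule for classifying a transplant.

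**The concern.** Items 7 to 9 are where the trial describes how DEB-TACE performs as a bridge to transplant. A planned transplant in a patient held within criteria and a rescue transplant for a liver that failed after the procedure are opposite results for that purpose. The safety sections recognise the difference; the efficacy items do not.

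The authors plainly saw that cause matters, because exception 2 turns on it. But that distinction decides only replacement and inclusion in the safety analysis, and it covers only the month after the first procedure. Section 3.2 allows up to four procedures, so a toxicity-driven transplant after a later one is not classified for items 7 to 9 at all. A reader of the item 7 curve could not tell a completed bridge from a rescue.

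**Working it through.** **Step 1. Follow one patient through the rules.** Take two listed, active patients who are both transplanted.

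| Rule | Planned transplant | Transplant for treatment-related decompensation |
|---|---|---|
| Item 7 | counted | counted |
| Item 8 | transplant excluded | transplant excluded |
| Exception 2, month after first DEB-TACE | replaced | retained |
| Section 14.1.3 | not in itself an SAE of this type | life-threatening SAE |

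In item 7 the two columns are identical. The second patient could appear in item 8 only through a separate inactivation before the transplant. In the window of exception 2, every retained transplant is toxicity-driven by construction. Item 9 is narrower, since it also requires down-staging, but it too is silent on cause.

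**Step 2. Reproduce the documents' rates.** The plan gives no size, power or threshold for items 7 to 9, so the inputs are the two cohorts in Section 1.2.

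- Conventional TACE: 6 urgent transplants in 252 patients = 2.4% (stated as 2%). Irreversible hepatotoxicity: 37/252 = 14.7% (stated as 15%). Deaths within 30 days: 5/252 = 2.0%.
- DEB-TACE at the same institution, patients within the proposed entry criteria: 0 urgent transplants in 37.

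**Step 3. Scale to 51 patients.**

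- Conventional TACE rate: 51 × 6/252 = 1.2 patients. Exact 95% interval for the rate is 0.9% to 5.1%, or 0.4 to 2.6 patients. Chance of at least one: 1 − (1 − 0.0238)^51 = 71%.
- DEB-TACE rate: expected 0. Exact two-sided upper 95% limit: 1 − 0.025^(1/37) = 9.5%, or 4.8 patients.

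If all such transplants meet item 7, separating them lowers it by about 2.4 percentage points at the first rate and by nothing at the second.

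**Step 4. Does toxicity raise or lower item 7?** Let t be the toxicity rate, u the chance of urgent transplant given toxicity, and q the transplant proportion without toxicity. The documents do not give q, so it is varied. If toxic patients who are not urgently transplanted are never transplanted:

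item 7 = (1 − t)q + tu, which exceeds q only when u > q.

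Take t = 14.7%. One value of u is 6/37 = 16%, assuming all six urgent transplants came from the 37 irreversible cases. Another is 6/11 = 55%, the urgent transplants as a share of urgent transplants plus 30-day deaths.

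| q | u | item 7 |
|---|---|---|
| 10% | 16% | 10.9% (up) |
| 30% | 16% | 28.0% (down) |
| 50% | 16% | 45.0% (down) |
| 30% | 55% | 33.6% (up) |
| 70% | 55% | 67.7% (down) |

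If the remaining toxic patients are still transplanted at rate q, item 7 always rises: with q = 30% and u = 16% it becomes 31.7%. The sign depends on quantities that the documents do not supply.

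**The case against.** **The event is not hidden.** It is an SAE, graded for causality (Section 14.2), reviewed by the monitoring committee (Section 13.5.3) and kept in the safety analysis, and persistent grade 4 liver dysfunction counts toward a stopping rule (Section 10.1.2). This stands, and it limits the harm. It does not correct the efficacy proportion. Adverse event reporting also ends at transplant (Section 14.3), and the stopping rule does not say how a patient transplanted before the month is over is counted.

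**The endpoints decide nothing.** They are secondary, have no threshold, and the plan never calls them success. The go/no-go rules use tumour response and toxicity. This stands.

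**The items are narrower than all transplants.** A reader might infer that any transplant counts. It does not: item 7 requires active waitlist status, item 9 also requires down-staging, and Section 4.2 admits patients who have only been screened for listing.

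**MELD is not the mechanism.** A reader might infer from Appendix 3 that toxicity raises MELD and so brings the transplant forward. The appendix only describes a calculator, items 7 to 9 do not refer to it, and no section says that MELD sets priority; Section 1.6 ties allocation to T2 criteria. Section 1.2 alone supports the link from decompensation to urgent transplant.

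**Attribution is imperfect.** Section 7.1 accepts that advancing cirrhosis can worsen liver toxicity, so an attribution of possibly related will catch some patients whose decompensation was not due to treatment. Scoring them as waitlist failures would misstate an outcome in which they did receive a liver. This stands, and is why a separate category is the better remedy.

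**Conclusion.** The classification gap is real and can be read directly from Section 12.3. Items 7 and 8 do not distinguish transplants by cause, and exception 2 retains only toxicity-driven transplants in the month after the first DEB-TACE.

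The effect is modest and uncertain: between no patients and a handful of the 51. The higher expected figure assumes that the conventional TACE rate carries over, yet that cohort had broader entry criteria (166 of the 252 met this study's, per Section 10.1.1) and a different technique. The 0/37 series is closer to the study population but too small to exclude several cases.

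Two stronger readings are not supported. One is that more toxicity improves the transplant result: toxicity also leads to death and delisting, and the sign turns on an unknown q. The other is that these cases could form up to 40% of transplants, which needs four of them among only ten. The documents give no expected number of transplants, although a typical wait of 1.5 to 2 years (Section 1.1) against one year of follow-up means that planned transplants may be few.

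This is worth correcting before analysis, but it does not threaten the trial's primary conclusions.

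**What to change.** Amend Section 12.3 as follows.

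1. In items 7 and 9, count only transplants that were not due to decompensation or other toxicity judged at least possibly related to DEB-TACE.
2. Report toxicity-driven transplants as their own category beside items 7 and 8, neither bridge nor dropout.
3. Extend the attribution in exception 2 from the month after the first procedure to every transplant during follow-up, recorded when the transplant occurs because patients then leave the study (Section 10.3).
4. Also show item 7 with all transplants combined, so that the influence of attribution is visible.
5. State how item 7's Kaplan-Meier analysis treats toxicity-driven transplants, death and delisting. Competing events are preferable to censoring, which would treat these patients as still able to reach a planned transplant.

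The cost is SAP wording and one attribution field per transplanted patient. The transplant proportion may look slightly less favourable, by about 2.4 points at the conventional TACE rate.

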Appendix 4 Modified RECIST

Table 2 Assessment of Target Lesion Response: Conventional RECIST and mRECIST Assessment for HCC Following the AASLD-JNCI Guideline

RECIST	mRECIST for HCC
CR = Disappearance of all target lesions	CR = Disappearance of any intratumoral arterial enhancement in all target lesions
PR = At least a 30% decrease in the sum of diameters of target lesions, taking as reference the baseline sum of the diameters of target lesions	PR = At least a 30% decrease in the sum of diameters of viable (enhancement in the arterial phase) target lesions, taking as reference the baseline sum of the diameters of target lesions
SD = Any cases that do not qualify for either partial response or progressive disease	SD = Any cases that do not qualify for either partial response or progressive disease
PD = An increase of at least 20% in the sum of the diameters of target lesions, taking as reference the smallest sum of the diameters of target lesions recorded since treatment started	PD = An increase of at least 20% in the sum of the diameters of viable (enhancing) target lesions, taking as reference the smallest sum of the diameters of viable (enhancing) target lesions recorded since treatment started

AASLD, American Association for the Study of Liver Diseases; JNCI, Journal of the National Cancer Institute; HCC, hepatocellular carcinoma; mRECIST, modified Response Evaluation Criteria in Solid Tumors; CR, complete response; PR, partial response; SD, stable disease; PD, progressive disease.

Appendix 5. DC Bead® Drug Delivery Embolization System Instructions for Use

DC Bead®

English
Doxorubicin

INSTRUCTIONS FOR USE

DC Bead®

Drug Delivery Embolisation System

STERILE • SINGLE USE ONLY • NON-PYROGENIC

■ DESCRIPTION:

DC Bead comprise a range of hydrogel microspheres that are biocompatible, hydrophilic, non resorbable, precisely calibrated and capable of loading doxorubicin. DC Bead is produced from polyvinyl alcohol and are available in the following size ranges:

Nominal Bead Size	Label Colour	Upon loading with doxorubicin, DC Bead undergo a slight decrease in size, up to 20% when loading at 25mg/ml.
100 – 300 µm	Yellow	
300 – 500 µm	Blue	
500 – 700 µm	Red	
700 – 900 µm	Green	

■ PRESENTATION:

- 10 ml glass vial.
- Each vial contains approximately 2 ml of DC Bead in non-pyrogenic, sterile, physiological buffered saline. Total volume of saline and DC Bead is approximately 8ml.
- The vial is stopper sealed by an aluminium cap equipped with a colour-coded lid.
- Each vial is intended for single patient use only. Do not resterilise. Discard any unused material.

■ INDICATIONS:

DC Bead are intended to be loaded with doxorubicin for the purpose of:

- Embolisation of vessels supplying malignant hypervascularised tumour(s).
- Delivery of a local, controlled, sustained dose of doxorubicin to the tumour(s).

■ CONTRAINDICATIONS – DC BEAD:

- Patients intolerant to vascular occlusion procedures.
- Vascular anatomy that precludes catheter placement or emboli injection.
- Presence or likely onset of vasospasm.
- Presence or likely onset of haemorrhage.
- Presence of severe atheromatous disease.
- Presence of feeding arteries smaller than distal branches from which they emerge.
- Presence of patent extra-to-intracranial anastomoses or shunts.
- Presence of collateral vessel pathways potentially endangering normal territories during embolisation.
- Presence of end arteries leading directly to cranial nerves.
- Presence of arteries supplying the lesion not large enough to accept DC Bead.
- Vascular resistance peripheral to the feeding arteries precluding passage of DC Bead into the lesion.
- Do not use DC Bead in the following applications:
 - i. Embolisation of non-malignant tumours.
 - ii. Embolisation of large diameter arteriovenous shunts (ie. where the blood does not pass through the arterial/capillary/venous transition but directly from artery to vein).
 - iii. Any vasculature where DC Bead Embolic Agent could pass directly into the internal carotid artery or other non-target territories.

Biocompatibles

Excellence in Interventional Oncology

CN00103.4

Biocompatibles UK Ltd is a
BTG International group company

■ CONTRAINDICATIONS – DOXORUBICIN:

- See doxorubicin package insert for contraindications regarding use.

WARNING: Studies have shown that DC Bead do not form aggregates and, as a result, penetrate deeper into the vasculature as compared to similarly sized PVA particles.

■ CAUTIONS:

- Do not use if the vial or packaging appear damaged.
- Select the size and quantity of DC Bead appropriate for the pathology to be treated.
- Embolisation with DC Bead should only be performed by a physician with appropriate interventional occlusion training in the region intended to be embolised.
- **Exceeding a loading dose of 37.5mg doxorubicin per 1ml DC Bead may lead to some systemic distribution of doxorubicin and related side effects.**

■ POTENTIAL COMPLICATIONS:

- Undesirable reflux or passage of DC Bead into normal arteries adjacent to the targeted lesion or through the lesion into other arteries or arterial beds.
- Non-target embolisation.
- Pulmonary embolisation.
- Ischaemia at an undesirable location.
- Capillary bed saturation and tissue damage.
- Ischaemic stroke or ischaemic infarction.
- Vessel or lesion rupture and haemorrhage.
- Neurological deficits including cranial nerve palsies.
- Vasospasm.
- Death.
- Recanalisation.
- Foreign body reactions necessitating medical intervention.
- Infection necessitating medical intervention.
- Clot formation at the tip of the catheter and subsequent dislodgement.

■ DRUG LOADING INSTRUCTIONS:

DC Bead is suitable for loading doxorubicin-HCl ONLY. Liposomal formulations of doxorubicin are not suitable for loading into DC Bead.

To obtain a final loading of 50mg doxorubicin per 2ml vial of DC Bead:

- i. Reconstitute a vial containing 50mg of doxorubicin with 2ml of sterile water for injection. Mix well to obtain a clear red solution (25mg/ml).
- ii. Remove as much saline as possible from a vial of DC Bead using a syringe with a small gauge needle.
- iii. Using a syringe and needle add the 2ml of reconstituted doxorubicin solution directly to the vial of DC Bead.
- iv. Agitate the DC Bead/doxorubicin solution occasionally to encourage mixing until the DC Bead is red. Although the solution retains a red colour, the doxorubicin will be loaded.
- v. Loading will take a minimum of 20 minutes for the smallest size DC Bead and up to 120 minutes for the largest size DC Bead.
- vi. Prior to use, transfer the DC Bead loaded with doxorubicin to a syringe and add an equal volume of non-ionic contrast media. Invert the syringe gently to obtain an even suspension of DC Bead.
- vii. A dose of up to 37.5mg doxorubicin per ml DC Bead can be loaded.
- viii. **The maximum recommended total dose of doxorubicin per procedure is 150mg.**

■ STORAGE OF DRUG LOADED DC BEAD:

- i. DC Bead loaded with doxorubicin may be stored for up to 24 hours in a fridge at 2-8°C in the presence or absence of non-ionic contrast media.

■ DELIVERY INSTRUCTIONS:

- Carefully evaluate the vascular network associated with the lesion using high resolution imaging prior to beginning the embolisation procedure.
- DC Bead are available in a range of sizes. Care should be taken to choose the appropriate size of DC Bead that best matches the pathology (ie. vascular target/vessel size) and provides the desired clinical outcome.
- Choose a delivery catheter based on the size of the target vessel. DC Bead can tolerate temporary compression of 20% to 30% in order to facilitate passage through the delivery catheter.
- Introduce the delivery catheter into the target vessel according to standard techniques. Position the catheter tip as close as possible to the treatment site to avoid inadvertent occlusion of normal vessels.
- DC Bead are not radio-opaque. It is recommended to monitor the embolisation under fluoroscopic visualization by adding the desired amount of contrast medium to the suspension fluid.
 - i. Take care to ensure proper suspension of the DC Bead in the contrast medium to enhance distribution during injection.
 - ii. Draw the DC Bead into a syringe needle of a size greater than or equal to 19 gauge (1.07 mm).
 - iii. Slowly inject DC Bead into the delivery catheter under fluoroscopic visualization while observing the contrast flow rate. Exercise conservative judgment in determining the embolisation endpoint.
- Upon completion of the treatment, remove the catheter while maintaining gentle suction so as not to dislodge DC Bead still within the catheter lumen.
- Discard any unused DC Bead loaded with doxorubicin.

■ CONSERVATION AND STORAGE:

- Store unopened DC Bead in a cool, dry and dark place in its original packaging.
- Use by the date indicated on the vial label.
- Do not freeze.

■ PACKAGE LABEL:

REF	Catalogue number	 Steam Sterilised	 Protect from moisture
LOT	Batch number/Lot number	 Use before/Expiry	 Attention see instructions for use
 Do not reuse		 Protect from light	 Do not freeze

